4.3.2. Other Endpoint(s) Analyses

Other endpoints will be summarised descriptively and based on the mITT analysis set. Categorical data will be summarized as the number and percentage of participants in each inhaler group (ELLIPTA or BREEZHALER).

4.3.2.1. Definition of endpoint(s)

Other endpoints are:

- Number of errors (critical and overall) made after reading the PIL(s), and, if necessary, after receiving further instruction from the HCP.
- Ease-of-use from questionnaire CCI [REDACTED]

4.3.2.2. Number of errors made

The number and percentage of participants who make at least one critical error will be presented by sequence (ELLIPTA/BREEZHALER or BREEZHALER/ELLIPTA) within each period and overall for each inhaler (ELLIPTA and BREEZHALER), by instruction:

- 0: after reading the PIL,
- 1: following the first instruction,
- 2: following the second instruction,
- 3: following the third (and final) instruction.

The number and percentage of participants who make at least one overall error will be presented in the same way as those who make at least one critical error.

In addition, the total number of critical errors and overall errors made will also be presented by instruction for each inhaler.

4.3.2.3. Ease-of-use questionnaire

The number and percentage of participants who rate the ease of using the inhaler as **CCI** will be presented for each ease-of-use attribute within the questionnaire:

- Ease of using the inhaler
- Telling how many doses are left in inhaler
- Learning how to use the inhaler
- Handling the inhaler
- Preparing the inhaler
- Holding the inhaler while using it

All model checking statistics will be assessed but not formally reported in a table, listing or figure.

4.4. Safety Analyses

The safety analyses will be based on the Safety Analysis Set for all Adverse Device Effects. As this is a placebo only inhaler study and no active drug is being prescribed, summaries and listings for all other safety analyses will be presented for all participants combined based on the Full Analysis Set.

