10.6. Appendix 6: Preference Questionnaires

[figure not shown]
Version 1 - Sequence A (ELLIPTA BREEZHALER) and Sequence C (BREEZHALER ELLIPTA)

[figure not shown]
CCI - This section contained Clinical Outcome Assessment data collection questionnaires or indices, which are protected by third party copyright laws and therefore have been excluded.

Version 2 - Sequence B (ELLIPTA BREEZHALER) and Sequence D (BREEZHALER ELLIPTA)

CCI - This section contained Clinical Outcome Assessment data collection questionnaires or indices, which are protected by third party copyright laws and therefore have been excluded.

10.7. **Appendix 7: ADEs, SADEs, and Device Deficiencies: Definition and Procedures for Recording, Evaluating, Follow-up, and Reporting in Medical Device Studies**

- The definitions and procedures detailed in this appendix are in accordance with ISO 14155 and European Medical Device Regulation (MDR) 2017/745 for clinical device research (if applicable).
- Both the investigator and the sponsor will comply with all local medical device reporting requirements for medical devices.
- The detection and documentation procedures described in this protocol apply to all GSK medical devices provided for use in the study (see Section 6.1.1 for the list of GSK medical devices).

10.7.1. **Definition of ADE**

ADE Definition

 • An adverse device effect (ADE) is an AE related to the use of an investigational medical device. This definition includes any AE resulting from insufficient or inadequate instructions for use, deployment, implantation, installation, or operation, or any malfunction of the investigational medical device as well as any event resulting from use error or from intentional misuse of the investigational medical device.

10.7.2. **Definition of SADE**

A SADE is any serious ADE that:
a. Led to death
b. Led to serious deterioration in the health of the participant, that either resulted in:

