To compare ease-of-use for ELLIPTA and BREEZHALER inhalers.	
Ease-of-use from questionnaire. This will be grouped as easy ^{CCI} [REDACTED] ^{CCI} [REDACTED] or difficult ^{CCI} [REDACTED] ^{CCI} [REDACTED]. The variables will include:
 
 • Ease of use rating • Telling how many doses are left in inhaler • Learning how to use the inhaler • Handling the inhaler • Preparing the inhaler • Holding the inhaler while using it.
To summarize ease-of-use for ELLIPTA and BREEZHALER inhalers.	
Ease-of-use from questionnaire ^{CCI} [REDACTED] ^{CCI} [REDACTED]). The variables will include the:
 
 • Ease of use rating • Telling how many doses are left in Inhaler • Learning how to use the inhaler • Handling the inhaler

	
 • Preparing the inhaler • Holding the inhaler while using it.
To compare the willingness to continue with the ELLIPTA and/or BREEZHALER inhaler.	Willingness to continue with the inhaler using a visual analogue scale (VAS) between 0 ^{CCI} [REDACTED] to 100 ^{CCI} [REDACTED]
To compare preference attributes for ELLIPTA and BREEZHALER inhalers.	Inhaler preference from questionnaire (ELLIPTA, BREEZHALER or no preference). The variables will include: 
 • Preferred inhaler, overall. • Number of steps to take the medication • Time needed to take the medication • How easy the inhaler is to use • Size of the inhaler • Comfort of the mouthpiece • Ease of opening the inhaler.
Safety	
To evaluate the safety of the ELLIPTA device and the BREEZHALER device.	Incidence of adverse device effects (ADEs)/serious adverse events (SAEs)/serious adverse device effects (SADES).

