4.4.2. Serious Adverse Events and Other Safety Reporting

Reporting of safety analyses includes the analysis of adverse device effects (ADEs), Serious AEs (SAEs), Serious ADEs (SADEs) and other significant ADEs will be based on GSK Core Data Standards.

Adverse events (AEs) will not be reported for this study. Instead, ADEs will be captured using the standard CDISC AE eCRF in conjunction with the Medical Device Deficiency eCRF. An ADE is defined as an AE for which the investigator classifies the relationship to Medical Device Deficiency for a non-serious adverse event as “Yes”, where the start date of the AE occurs on the same date as the device deficiency.

Adverse events to identify ADEs will be coded using the standard Medical Dictionary for Regulatory Affairs (MedDRA dictionary), with the maximum severity of each AE determined by

the investigator (as mild, moderate or severe). A Standardised MedDRA Query (SMQ) will be used to identify all COVID-19 AEs.

An overview summary of ADEs, including counts and percentages of participants with any ADE and ADEs leading to discontinuation of the study inhaler (and therefore withdrawal from the study) will be produced. The summary tables will be displayed by SOC and PT.

The number and percentage of participants experiencing at least one ADE during the study, in which the medical device is used, will be summarised by each inhaler separately. Additionally, summaries of the number and percentage of participants with any ADEs by maximum severity will be produced. If an adverse event severity is missing, the severity is to be populated as “UNKNOWN”.

The frequency and percentage of ADEs will be summarized and displayed in two ways:
1) in descending order by SOC and PT and 2) in descending order by PT only.

Common ADEs, defined as $\geq 3\%$ (prior to rounding) in any inhaler group, will be reported. The summary table will be displayed by PT only.

A worst-case scenario approach will be taken to handle missing relatedness data, i.e. the summary table will include events with the relationship to study inhaler as “Yes” or missing. The summary table will be displayed by SOC and PT.

The number and percentage of participants experiencing at least one SAE during the study will be summarised.

The number and percentage of participants experiencing at least one SADE during the study, in which the medical device is used, will be summarised by each inhaler separately.

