Listings will be presented separately for SAEs and SADEs. All SAEs, SAEs related to study treatment, fatal SAEs, fatal SAEs related to study treatment, all SADEs, fatal SADEs, and fatal SADEs will be produced. In addition, fatal and non-fatal SAEs, and, fatal and non-fatal SADEs will be reported separately.

A study treatment-related SAE is defined as an SAE for which the investigator classifies the relationship to study treatment (i.e. placebo) as “Yes”. A worst-case scenario approach will be taken to handle missing data, i.e. the summary table will include events with the relationship to study treatment as “Yes” or missing. The summary tables will be displayed by SOC and PT.

An SADE is defined as an SAE for which the investigator classifies the relationship to Medical Device Deficiency for a serious adverse event as “Yes”. A worst-case scenario approach will be taken to handle missing data, i.e. the summary table will include events with the relationship to study treatment as “Yes” or missing. The summary tables will be displayed by SOC and PT.

The incidence of AEs and SAEs (Fatal and Non-Fatal) of COVID-19, COVID-19 AEs leading to study inhaler discontinuation, COVID-19 AEs leading to study withdrawal, and COVID-19 AEs by maximum severity, will be obtained from the standard AE and SAE summaries.

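### SAP 4.4 pools SAEs over both inhalers although the safety objective is about each device, so if any SAE occurs the planned percentage cannot be assigned to a device

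*SAP*

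**What the plan says.** SAP 1.1.1 gives the safety objective as "To evaluate the safety of the ELLIPTA device and the BREEZHALER device", and its endpoint begins "Incidence of adverse device effects (ADEs)/serious adverse events (SAEs)/serious adverse device effects". Protocol 3 says the same.

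SAP 4.4 puts adverse device effects on the Safety set. For the rest, it gives the reason "As this is a placebo only inhaler study and no active drug is being prescribed" and then states that "summaries and listings for all other safety analyses will be presented for all participants combined based on the Full Analysis Set".

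SAP 4.4.2 follows this. For SAEs: "The number and percentage of participants experiencing at least one SAE during the study will be summarised", with no split by inhaler. ADEs are summarised for each inhaler, and for SADEs a count and proportion of those "experiencing at least one SADE during the study, in which the medical device is used, will be summarised by each inhaler separately".

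The two documents define device-related events differently. SAP 4.4.2: "An SADE is defined as an SAE for which the investigator classifies the relationship to Medical Device Deficiency". Protocol 10.7.1: "An adverse device effect (ADE) is an AE related to the use of an investigational medical device"; under protocol 10.7.2 an SADE is a serious ADE.

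Protocol 9.4.3 promises a summary by inhaler for ADEs only, listings for SAEs and SADEs, and narratives for deaths, SAEs and SADEs.

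**The concern.** The objective names two devices and SAE incidence is one of three endpoints serving it, yet the SAE summary has no device dimension. The absence of active drug would justify pooling if the question were about a drug. Here the question is about inhalers that deliver powder. The risk table in protocol 2.3.1 lists paradoxical bronchospasm after inhaling and allergic reaction to the lactose excipient, and placebo status removes neither.

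The crossover design makes the loss complete for the summary figure. Each participant uses both inhalers on one day, so a count of participants with an SAE does not show which inhaler came before the event. What is at stake is what the clinical study report can state about each device if an SAE occurs. Power and the efficacy analyses are not involved.

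**Working it through.** **Inputs.** 114 randomised, about 114 evaluable, no withdrawals expected (SAP 5). Both inhalers received at Visit 1 (SAP 1.2). No expected SAE rate is given in the documents, so the counts below are illustrations.

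**The plan's own figure.** The 114 serves here only as the denominator, and it reproduces. Per sequence, n = (z₀.₉₇₅ + z₀.₉₀)² × SD² / (ln OR)² = (1.960 + 1.282)² × 2.785² / (ln 0.3)² = 56.22, rounded up to 57; two sequences give 114. Nothing below changes it.

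**No SAE.** If all 114 use both inhalers, a pooled 0/114 means 0/114 after ELLIPTA and 0/114 after BREEZHALER. The exact upper limit of the two-sided 95% interval is 1 − 0.025^(1/114) = 3.18% for each device (one-sided: 1 − 0.05^(1/114) = 2.59%). Pooled and split displays carry the same information.

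**One or more SAEs.** Suppose k participants each have one SAE with onset after first inhaler use. There are k + 1 ways to divide them between the inhalers, and the pooled percentage is the same for all of them.

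| SAEs | Pooled | Possible ELLIPTA / BREEZHALER |
|---|---|---|
| 1 | 1/114 = 0.88% | 0/0.88%; 0.88%/0 |
| 2 | 2/114 = 1.75% | 0/1.75%; 0.88%/0.88%; 1.75%/0 |

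Onset before either inhaler adds further possibilities. Protocol 8.3.1 collects SAEs from consent, and Visit 1 may follow up to 30 days later. The same section also sends medical occurrences before the start of study intervention to medical history, so the handling of an early SAE is not clear.

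**Does the by-inhaler SADE table fill the gap?** Only in part.
- Protocol 10.7.1 asks whether the event is related to use of the device. SAP 4.4.2 asks whether it is related to a Medical Device Deficiency.
- Protocol 10.7.3 counts use errors as deficiencies, so many device-related events qualify under both.
- Serious bronchospasm after correct use of a working inhaler need not involve a deficiency. It is a foreseeable case: bronchospasm is in the risk table, and protocol 10.2.2 gives intensive treatment for allergic bronchospasm as an example of a serious event.
- Such an event meets the protocol definition of an SADE if judged related to use, but not the SAP definition. It would then be summarised only in the pooled SAE figure.

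**Can the listing fill it?** SAP 4.4.2 lists SAEs, but the SAP does not say whether the listing shows inhaler or period. Onset date alone cannot separate two inhalers used on the same day.

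**The case against.** The other side has a good case. SAEs do not rest on one percentage. They are listed, the investigator must assess causality for each one with regard to timing (protocol 10.2.4), and protocol 9.4.3 requires narratives. With a handful of events at most, those outputs tell the reader more than a split percentage. SADEs are given by inhaler, and SAP 4.4.2 counts missing relatedness as related. The safety objective says evaluate where the efficacy objectives say compare, so giving the two device-related endpoints by inhaler and all-cause SAEs as a study total is a defensible reading. SAP 1 leaves display details to a separate specification that is not available here. Finally, assignment to the last-used inhaler may credit a delayed reaction from the first inhaler to the second.

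Most of this stands, and it rules out three stronger readings that a reader might infer:
- That a pooled zero says nothing about either device. It gives the same 3.18% bound for each, provided everyone used both.
- That any single SAE would be unattributed. Narratives, causality assessments and listings may well identify the inhaler.
- That pooling breaks a protocol commitment. Protocol 9.4.3 promises no SAE table by inhaler; SAP version 2 went further by adding SAE and SADE summary tables.

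Two things remain. The reason given for pooling does not address devices, and the narrower SADE definition leaves a class of use-related serious events with no summary by inhaler.

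**Conclusion.** The point holds, and it is minor. The SAE endpoint, as summarised, does not address the device objective once any SAE occurs; with none, nothing is lost. It is too strong to say that the SAE part of the objective cannot be answered at all, because case-level outputs remain. The gap is in the summary, and it matters most for a serious event related to inhaler use without a recorded deficiency.

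This rests on three assumptions: few or no SAEs occur in a one-day placebo handling study; essentially all participants use both inhalers; and the display specification, which is not available here, does not already split SAEs by inhaler against the SAP's wording.

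**What to change.** In SAP 4.4 and 4.4.2:
1. Summarise SAEs by the inhaler in use or last used at onset, with participants who used that inhaler as the denominator. Add a separate column for onset before first inhaler use, and keep the combined total.
2. Show inhaler and period at onset in the SAE listing.
3. Align the SADE definition with protocol 10.7, so that it covers events related to use of the device. The SAP's ADE definition carries the same restriction to a deficiency and should be changed with it.
4. Name SADEs beside ADEs in the SAP 4.4 exception, to match SAP 4.1.1 and 4.4.2.
5. Footnote that attribution to the last-used inhaler is approximate, because the second inhaler follows on the same day with a break of at most 30 minutes.

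The cost is SAP wording and one table shell. Onset time or period must be captured on the SAE page, and relatedness to device use if the form records only relatedness to a deficiency. No more participants are needed.

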4.4.1. Extent of Exposure

This is a one-day inhaler-handling study in which all participants will receive placebo.

4.4.2. Serious Adverse Events and Other Safety Reporting

Reporting of safety analyses includes the analysis of adverse device effects (ADEs), Serious AEs (SAEs), Serious ADEs (SADEs) and other significant ADEs will be based on GSK Core Data Standards.

Adverse events (AEs) will not be reported for this study. Instead, ADEs will be captured using the standard CDISC AE eCRF in conjunction with the Medical Device Deficiency eCRF. An ADE is defined as an AE for which the investigator classifies the relationship to Medical Device Deficiency for a non-serious adverse event as “Yes”, where the start date of the AE occurs on the same date as the device deficiency.

Adverse events to identify ADEs will be coded using the standard Medical Dictionary for Regulatory Affairs (MedDRA dictionary), with the maximum severity of each AE determined by

the investigator (as mild, moderate or severe). A Standardised MedDRA Query (SMQ) will be used to identify all COVID-19 AEs.

An overview summary of ADEs, including counts and percentages of participants with any ADE and ADEs leading to discontinuation of the study inhaler (and therefore withdrawal from the study) will be produced. The summary tables will be displayed by SOC and PT.

The number and percentage of participants experiencing at least one ADE during the study, in which the medical device is used, will be summarised by each inhaler separately. Additionally, summaries of the number and percentage of participants with any ADEs by maximum severity will be produced. If an adverse event severity is missing, the severity is to be populated as “UNKNOWN”.

The frequency and percentage of ADEs will be summarized and displayed in two ways:
1) in descending order by SOC and PT and 2) in descending order by PT only.

Common ADEs, defined as $\geq 3\%$ (prior to rounding) in any inhaler group, will be reported. The summary table will be displayed by PT only.

A worst-case scenario approach will be taken to handle missing relatedness data, i.e. the summary table will include events with the relationship to study inhaler as “Yes” or missing. The summary table will be displayed by SOC and PT.

The number and percentage of participants experiencing at least one SAE during the study will be summarised.

The number and percentage of participants experiencing at least one SADE during the study, in which the medical device is used, will be summarised by each inhaler separately.

Listings will be presented separately for SAEs and SADEs. All SAEs, SAEs related to study treatment, fatal SAEs, fatal SAEs related to study treatment, all SADEs, fatal SADEs, and fatal SADEs will be produced. In addition, fatal and non-fatal SAEs, and, fatal and non-fatal SADEs will be reported separately.

A study treatment-related SAE is defined as an SAE for which the investigator classifies the relationship to study treatment (i.e. placebo) as “Yes”. A worst-case scenario approach will be taken to handle missing data, i.e. the summary table will include events with the relationship to study treatment as “Yes” or missing. The summary tables will be displayed by SOC and PT.

An SADE is defined as an SAE for which the investigator classifies the relationship to Medical Device Deficiency for a serious adverse event as “Yes”. A worst-case scenario approach will be taken to handle missing data, i.e. the summary table will include events with the relationship to study treatment as “Yes” or missing. The summary tables will be displayed by SOC and PT.

The incidence of AEs and SAEs (Fatal and Non-Fatal) of COVID-19, COVID-19 AEs leading to study inhaler discontinuation, COVID-19 AEs leading to study withdrawal, and COVID-19 AEs by maximum severity, will be obtained from the standard AE and SAE summaries.

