
 • A life-threatening illness or injury. The term 'life-threatening' in the definition of 'serious' refers to an event in which the participant was at risk of death at the time of the event. It does not refer to an event, which hypothetically might have caused death, if it were more severe. • A permanent impairment of a body structure or a body function. • Inpatient or prolonged hospitalization. Planned hospitalization for a pre-existing condition, or a procedure required by the protocol, without serious deterioration in health, is not considered an SADE. • Medical or surgical intervention to prevent life-threatening illness or injury or permanent impairment to a body structure or a body function
c. Led to fetal distress, fetal death or a congenital abnormality or birth defect
d. Is a suspected transmission of any infectious agent via a medicinal product

Definition

- A SADE is defined as an adverse device effect that has resulted in any of the consequences characteristic of a serious adverse event.
- Any device deficiency that might have led to an SAE/SADE if appropriate action had not been taken, intervention had not occurred, or circumstances had been less fortunate.

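### SAP 4.4.2 ties ADEs and SADEs to a Medical Device Deficiency while Protocol 10.7.1 and 10.7.2 tie them to use of the device; the undeclared narrower definition can keep events out of the by-inhaler safety tables

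*SAP*

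**What the plan says.** **Protocol.** Section 10.7.1 states: "An adverse device effect (ADE) is an AE related to the use of an investigational medical device". It then names cases that fall within this: poor instructions, malfunction, use error and intentional misuse. Section 10.7.2 builds on it: "A SADE is defined as an adverse device effect that has resulted in any of the consequences characteristic of a serious adverse event". The same box has a second limb, for deficiencies that might have led to a serious event had circumstances been less fortunate. Section 10.7.3 defines a device deficiency separately, as an inadequacy of the device; malfunctions and use errors are among its examples. Section 9.4.3 requires all ADEs to be summarised by inhaler.

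**SAP.** Section 4.4.2 says that AEs will not be reported and that ADEs will be captured instead. Its ADE definition reads: "An ADE is defined as an AE for which the investigator classifies the relationship to Medical Device Deficiency for a non-serious adverse event"; the answer has to be Yes. A timing condition is then attached: "where the start date of the AE occurs on the same date as the device deficiency". Its SADE definition reads: "An SADE is defined as an SAE for which the investigator classifies the relationship to Medical Device Deficiency for a serious adverse event"; here too the answer has to be Yes. It plans ADE and SADE summaries for each inhaler separately. For the rest of safety, SAP 4.4 says that "summaries and listings for all other safety analyses will be presented for all participants combined based on the Full Analysis Set".

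On missing relatedness, SAP 4.4.2 has two rules. For ADEs, "the summary table will include events with the relationship to study inhaler as" Yes or missing; for SADEs, "the summary table will include events with the relationship to study treatment as" Yes or missing. SAP 4.7 lists one change from the protocol, the renaming of the performance evaluable set.

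**The concern.** The safety objective is to evaluate each device by the incidence of ADEs, SAEs and SADEs. The by-inhaler tables are the ones that answer it, and the definition decides what enters them. A deficiency is a property of the device, whereas an ADE is something that happens to a participant. Making the first a condition for the second narrows the class.

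Two things follow. An event that the protocol counts as an ADE or SADE may not be shown against the inhaler that was in use. In addition, the programmer has three relationship items to choose from: to the deficiency, to the study inhaler and to the study treatment. No rule covers a missing value in the one that decides the class.

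**Working it through.** No figure in the plan is at issue, so the check sets the definitions side by side and runs cases through them.

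**Conditions for each class**

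| | Protocol 10.7.1 and 10.7.2 | SAP 4.4.2 |
|---|---|---|
| ADE | AE related to device use | Non-serious AE, relationship to a deficiency is Yes, same start date as the deficiency |
| SADE | ADE with a serious consequence | SAE, relationship to a deficiency is Yes |
| Deficiency needed? | No | Yes |
| Field in the missing-data rule | None given | Study inhaler (ADE); study treatment (SADE) |

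**Cases**

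1. *Non-serious event after a malfunction or use error, deficiency recorded the same day.* An ADE under both documents.
2. *Non-serious event judged related to device use, no deficiency recorded*, for example after correct use of a sound inhaler. An ADE under the protocol. It does not meet the SAP definition. Since the SAP does not report AEs in general, the only other planned display that could hold it is the table keyed to study inhaler. The SAP does not say whether that table is limited to SAP-defined ADEs.
3. *Serious event judged related to device use, no deficiency recorded.* A SADE, and so also an ADE, under the protocol. Not a SADE under the SAP definition. It stays in the SAE summary and listings, which SAP 4.4 pools over inhalers.
4. *Deficiency-relationship item missing.* Neither missing-data rule names this item, so the SAP does not settle the class.

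**Which condition does the work.** The Schedule of Activities collects events only until the last assessment at Visit 1, and both inhalers are tested at that visit. The same-date clause will therefore seldom exclude an event by itself. The deficiency link is what excludes.

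**Is it declared?** SAP 4.7 is the place for departures from the protocol. Its table holds only the analysis-set name.

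**Scale of one omission.** This assumes that all 114 planned participants use each inhaler.

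- One participant is 1/114 = 0.88 percentage points of displayed incidence for that inhaler.
- The common-ADE table takes terms at 3% or more in any inhaler group. Three participants give 3/114 = 2.63%, below the cut; four give 4/114 = 3.51%, above it. Losing one of four would remove the term from that table.

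These figures show the effect of a single omission. They do not say how many there would be.

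**The case against.** **Overlap.** The cases named in Protocol 10.7.1 come close to what 10.7.3 counts as deficiencies, and 10.7.3 also covers inadequate safety or performance. Most device-related events might therefore have a deficiency recorded. This stands and limits the point to events with none. It does not make the definitions equivalent.

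**Other outputs.** A reader might infer that any event without a deficiency vanishes. The documents do not support that. Serious events remain in the pooled SAE summary, listings and narratives, and the tables keyed to study inhaler or study treatment may pick up others. The supported statement is that events can be missing from the by-inhaler tables.

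**Attribution.** Protocol 2.3.1 names wheeze after inhaling as a risk. An investigator may attribute it to the inhaled placebo and not to the device. It would then not be an ADE under the protocol either, so the example counts only if it is judged device-related.

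**Unseen material.** The SAP wording reads like an eCRF item, and the SAP leaves data-handling detail to the Output and Programming Specification. Neither that specification nor the eCRF was available, and either could soften the consequence in practice. The SAP text would still differ from the protocol.

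**Estimating the count.** Protocol 2.3.1 gives a frequency below 1/10,000 for paradoxical bronchospasm, and a reader might infer an upper limit from it. It does not serve as one: it is post-marketing data for an active product, its unit is not stated, and it covers one event type whether or not judged device-related. Nor is the number of inhalations fixed, since BREEZHALER checklist steps 9 and 11 call for repeats within an attempt.

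**Version history.** A reader might take its silence as evidence of an undeclared change. It records only what changed between SAP versions 1 and 2, so its silence shows nothing. Only SAP 4.7 bears on the question.

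**Conclusion.** The conflict is established from the text. The SAP makes a device deficiency a condition for ADEs and SADEs, the protocol does not, and SAP 4.7 does not say so. Followed as written, the SAP can leave protocol-defined events out of the by-inhaler tables, and its missing-data rules point to fields other than the one that decides the class.

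The size is unknown, because the documents give no rate of device-related events without a deficiency. The consequence rests on two assumptions: that at least one such event occurs, and that the table keyed to study inhaler is limited to SAP-defined ADEs (for non-serious events). The primary endpoint is not affected.

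A reader might also infer that the condition favours one inhaler, since Protocol 6.1.1 and the opening of 10.7 speak of GSK devices when describing deficiency documentation. Sections 8.3.8 and 8.3.8.4 extend it to the devices provided for the study, so the documents do not support a directional claim.

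This should be corrected before the safety tables are programmed; it does not threaten the main conclusion of the trial.

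**What to change.** In SAP 4.4.2:

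- Derive ADEs from the investigator's judgement of relationship to use of the ELLIPTA or BREEZHALER device, as in Protocol 10.7.1.
- Derive SADEs as ADEs that meet a seriousness criterion, as in Protocol 10.7.2. Summarise both by inhaler.
- Remove the deficiency and same-date conditions from the definitions, and show deficiency-linked events as a subset.
- List separately any deficiency that might have led to an SAE or SADE, so that the second limb of the 10.7.2 box is covered.
- Apply the missing-counts-as-related rule to that same device-relationship field for both classes.

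If the sponsor prefers the narrower definitions, declare and justify them in SAP 4.7.

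The cost is SAP wording and table programming. SAP 4.4.2 implies that a relationship-to-inhaler item is collected; if it is not, one eCRF item is needed. Sample size, visits and the primary analysis do not change.
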